Participants may withdraw from the study at any time without impact to their care. They may also be discontinued from the study at the discretion of the Investigator for lack of adherence to intervention or study procedures or visit schedules or AEs. The Investigator may also withdraw subjects who violate the study plan, to protect the subject for reasons related to safety or for administrative reasons. It will be documented whether or not each subject completes the study. Participants who withdraw early will not be compensated for research activities they did not yet complete.

6. Vulnerable Populations:

Children, pregnant women, fetuses, neonates, or prisoners are not included in this research study.

7. Populations vulnerable to undue influence or coercion:

The following populations will not be included in the study: children, prisoners, pregnant women, mentally disabled persons, or economically or educationally disadvantaged persons.

STUDY DESIGN:

This study is funded by NIH Grant # 3R01NR018196 - 02W1. In the proposed RCT we will enroll adults who are informal caregivers of adults with behavioral variant frontotemporal degeneration (bvFTD) and the bvFTD patients they care for. The study focuses on the caregivers, but we will also enroll the bvFTD patients to address our exploratory aim. We will seek bvFTD patient consent to review their medical records for factors anticipated to add to the demand of caregiving (e.g., dementia severity on mCDR).

Caregivers must be informal caregivers of patients with a confirmed diagnosis of bvFTD. They will be screened with the 10-item Health Self-Care Neglect scale; we will enroll only those who are poor in selfcare using a cut-point of 2 based on our pilot study. Caregivers must be able to provide informed consent (speak English, see, hear, cognitively intact) and complete the protocol. We will exclude caregivers with cognitive impairment because we anticipate that they would have difficulty completing the intervention. We will exclude anyone with untreated major psychiatric illness such as psychosis. Anyone who

is planning to move out of the area will not be enrolled. Anyone in a competing trial testing a support intervention also will be excluded. In this way, we anticipate enrolling only caregivers who are able to provide true informed consent and those who will potentially benefit from the intervention.

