Fully eligible caregivers who provide informed consent will complete the baseline assessment before being randomized to study arm. The Project Manager will open a numbered sealed envelope, prepared by the team in advance, which assigns caregivers to their study arm. The Project Manager will then notify the study staff and participants of their group assignment (ViCCY or HI only) by telephone, email or message. The Project Manager will notify the study staff and participants of their group assignment (ViCCY or HI only) by telephone, email or message, as preferred by the individual. Although balance in sample size can be achieved with block randomization, the groups may not be fully comparable on other factors. Initial comparison of the groups will allow us to control for important covariates in the analyses. Investigators and all staff involved in collecting assessment data will be blinded to group assignment until after the data are locked. The Health Coaches providing the intervention and the caregiver participants will not be blinded. All baseline data will be collected prior to randomizing. Timing of follow-up assessments will be based on day of randomization

4. Administration of Surveys and/or Process:

We will enroll 30 informal bvFTD caregivers and the bvFTD patients for whom they care. After collecting baseline data, we will block randomize the caregivers 1:1 to the intervention or control group, stratifying randomization by caregiver sex and relationship to the patient (e.g., spouse, adult child) factors known to influence caregiving burden, perceived stress, and receptivity to the intervention.

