We will provide tablet devices with wireless network access and connect caregivers in both conditions to the Internet so they can access the Internet site providing Health Information (HI) content for 6 months of the study. A data plan will be provided and is included on the tablets. Research staff will provide instruction on how to use the tablet and how to access the HI website. A research diary will also be provided to aid tracking of healthcare resources used and costs. Participating caregivers in both study arms will be encouraged to spend at least 30 minutes weekly using the Internet modules or books for six months. Those who choose to use books rather than the website will be asked to keep track of the number of book chapters reviewed each month. Use of the website or book chapters will be used as a measure of fidelity in both arms. After six months, we will collect all tablet devices (both groups) to minimize bleeding of the intervention into the follow-up period, and we will continue to track use of the website to identify if bleeding occurs.

In addition to augmented standard care HI, caregivers randomized to ViCCY will receive 10 front-loaded sessions of virtual health coaching by trained RNs over the first 6 months with content based on the theoretical framework and our prior research. Health coaching sessions will be provided through the tablets via Zoom conferencing software. Sessions are weekly initially and decrease in frequency over time. Because maintaining contact is important to the success of stress reduction interventions, the assigned Health Coaches will check in with caregivers between intervention sessions. We will offer booster sessions to any caregiver in the ViCCY arm who wishes to receive additional support during the 6-month intervention interval. We will track the number of sessions and test for differential effectiveness based on the dose received. If a brief check-in call becomes an intervention session, it will be tracked for use in analysis. We will mail monthly newsletters to maximize retention.

5. Data Management:

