A separate database will contain PHI and the link to the assigned patient identifier. Only the PI and the research staff will be able to access the PHI data. This information will be maintained by the PI upon the completion of this study; however, this data will not be shared or identified for secondary use without IRB approval. Data from the participating subjects will be stored in a password protected limited access human subject research database. Original source records will be maintained in locked offices.

3. Genetic Testing:

Not applicable

4. Use of Deception:

None

5. Statistical Analysis:

All analyses will use an intent-to-treat approach. Descriptive statistics will be used to characterize the sample, with measures of central tendency and variation for continuous measures, and frequencies and percentages for categorical variables. Distributional properties will be examined to determine if variance stabilizing or normalizing transformations should be applied. Non-inferential interim analyses will be performed to ensure data collection and archiving procedures are operating correctly. Outliers will be assessed by visual inspection and checked for accuracy. Once the database is locked, comparisons by group will assess for balance and identify multi-collinearity and areas requiring statistical adjustment. For comparisons involving continuous variables, homoscedasticity will be evaluated using Levines tests. Normality will be assessed using Shapiro-Wilk tests. Should violations emerge, transformations will be applied, or nonparametric tests used.

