To assess changes in each of the primary and secondary outcomes over time, separate mixed effects regression models will be generated with SAS Proc Mixed. We are not powered for secondary outcomes (e.g., stress, coping, health status), but we will examine effect sizes and confidence intervals (CIs) to determine if lack of power is driving nonsignificant results. Mixed models can account for correlation between repeated measures and handle non-excessive MAR or MCAR data better than traditional models and allow for use of time-independent and time-dependent covariates. Both random slopes and random intercepts will be modeled to represent deviations from the average, or fixed-effect, slope over time and intercept, respectively. REML will be used for parameter estimation and the most appropriate covariance structure will be examined. Scores will be analyzed as repeated observations, with mean-centered baseline outcome scores serving as a covariate. Other predictor variables will include group, assessment time, and the interaction of group time (primary effect of interest). Baseline measures and group will be analyzed as time-independent covariates. The evaluation of differences in outcome profiles over time according to group will rely on the group x time interaction terms, while differences by the balancing

variables will rely on the mixed-effects modeling of higher order interaction terms. Statistical significance for individual intervention contrasts will be evaluated for each outcome, applying the Benjamini & Hochberg method to control for the type I error rate at 5%. The Akaike information criterion (AIC) will be used to evaluate overall model fit and to select the best-fitting longitudinal change pattern. We expect the groups to be balanced on baseline characteristics due to randomization; however, imbalances that occur by chance will be adjusted for in all analyses. To evaluate patient outcomes (Aim 2) over time we will use mixed effects regression modeling. As described above, scores will be analyzed as repeated observations, with mean-centered baseline outcome scores serving as a covariate. Other predictor variables will include time-dependent caregiver variables, assessment time, and the corresponding two-way interaction term (primary effect of interest).

RISK/BENEFIT ASSESSMENT:

1. Risks:

Protection Against Risk:

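### The planned test of effectiveness by number of coaching sessions received uses an unrandomised exposure in about 15 caregivers, so its result is confounded and cannot support a dose claim

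*Combined protocol and SAP*

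**What the plan says.** METHODS, 4. Administration of Surveys and/or Process sets the planned dose: "caregivers randomized to ViCCY will receive 10 front-loaded sessions of virtual health coaching by trained RNs over the first 6 months". It then allows that dose to vary. On request: "We will offer booster sessions to any caregiver in the ViCCY arm who wishes to receive additional support during the 6-month intervention interval". Through contact between sessions: "If a brief check-in call becomes an intervention session, it will be tracked for use in analysis". It commits to an analysis: "We will track the number of sessions and test for differential effectiveness based on the dose received".

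METHODS, 3. Method for Assigning Subjects to Groups allocates caregivers to ViCCY or HI only, and adds: "The Health Coaches providing the intervention and the caregiver participants will not be blinded".

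STUDY PROCEDURES, 5. Statistical Analysis opens with "All analyses will use an intent-to-treat approach". Its caregiver models contain group, time, their interaction and the baseline outcome score. It has no dose variable, no model for the dose test, and no label marking that test as exploratory.

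**The concern.** A test of effectiveness by dose received asks whether caregivers who had more sessions did better because they had more sessions. Randomisation does not answer that question here, because nobody is randomised to a number of sessions. Every ViCCY caregiver is assigned the same 10, so the test can use only departures from 10. These departures come from caregivers and coaches who know the assignment, during the same six months in which the outcome develops.

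Missed sessions may reflect low motivation or heavy burden. Boosters and converted calls may reflect need. Either can relate to self-care at 6 months whatever coaching does. Motivation would make extra sessions look helpful; need would make them look useless or harmful.

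Missing data may add to this. Early Withdrawal of Subjects says of participants: "They may also be discontinued from the study at the discretion of the Investigator for lack of adherence to intervention or study procedures". METHODS, 6. Subject Follow-up ends data collection at withdrawal. Caregivers with few sessions may therefore also lack a 6-month outcome.

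At stake is the trial's statement, if it makes one, about whether the number of sessions matters.

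**Working it through.** **1. Is there a plan figure to reproduce?** Not for this test. The stated power of over 90% (Target Population and Accrual) refers to the group comparison on the Self-Care Inventory with 15 per arm. It comes without an effect size or SD and does not carry over to a dose test within one arm.

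**2. How many caregivers inform the test?** 30 are randomised 1:1, and HI caregivers receive no coaching sessions. Dose varies among 30 / 2 = 15 caregivers, fewer after dropout.

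**3. Precision.** For a sample correlation of zero, the Fisher 95% limits are ± tanh(1.96 / √(n − 3)). With n = 15: 1.96 / √12 = 0.566, and tanh(0.566) = 0.51. The interval is -0.51 to 0.51.

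**4. Detectable size.** For 80% power at two-sided 5%, the true correlation must be tanh((1.960 + 0.842) / √12) = tanh(0.809) = 0.67. For 90% power it is tanh((1.960 + 1.282) / √12) = tanh(0.936) = 0.73.

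**5. Bias with no true dose effect.** Let one unmeasured trait U correlate a with session count D and b with the 6-month outcome Y, with no effect of D on Y: D = aU + √(1 − a²)e₁ and Y = bU + √(1 − b²)e₂. The induced correlation between D and Y is a × b. The values of a and b are assumptions; the documents give none. Results are from 200,000 simulated samples of 15, with a two-sided 5% test:

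| a, b | a × b | mean sample r | rejections |
|---|---|---|---|
| 0, 0 | 0 | 0.00 | 5.0% |
| 0.3, 0.3 | 0.09 | 0.09 | 6.2% |
| 0.5, 0.5 | 0.25 | 0.24 | 14.5% |
| 0.7, 0.7 | 0.49 | 0.48 | 48% |

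If a is made negative, the correlation changes sign and the rejection rates are essentially the same. Nothing in the documents settles which sign applies.

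**6. Would baseline adjustment remove it?** Suppose the dose test also adjusted for a baseline score that correlates 0.7 with U (a further assumption). The rejection rates for 0.3, 0.5 and 0.7 become about 5%, 8% and 21%. The bias shrinks but does not vanish, and the adjustment would not deal with need that changes after baseline. The plan does not tie its baseline covariate to the dose test.

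**7. The two statements side by side.** One section tests effectiveness by what was received. The other says that every analysis compares caregivers as assigned. Both cannot hold as written.

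**The case against.** The strongest case against is that this is a minor side analysis. It appears in none of the aims or hypotheses and not in the statistical section. The 10-session dose is justified from pilot data and literature, not from this test, and nothing says that the result will be presented as causal. The correlations above are assumed, and at 0.3 the rejection rate is close to nominal. All of that is fair and limits the weight of the point. It does not remove it: the plan promises a test of effectiveness, not a description. In the same section, website and book use is treated as a fidelity measure, so descriptive wording was available.

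A reader might infer several stronger things that the documents do not support:

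- **That scheduled sessions, boosters and converted calls are added into one score.** No section says so, and the separate sentence on converted calls is compatible with identifying them separately.
- **That the direction of bias is known.** The links to motivation and need are plausible, not documented.
- **That a false dose finding would set the session number in the next study.** Subject Follow-up describes that study as one of longer-term effects of ViCCY versus HI.
- **That an instrumental-variable estimate, with assignment as the instrument, would rescue the analysis.** It requires assignment to act only through sessions. Check-ins between sessions and unblinded, self-reported outcomes make that implausible. With no sessions in HI, the ratio largely rescales the intention-to-treat difference and says nothing about differential effect by dose.

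**Conclusion.** The point holds, for this secondary analysis only. As written, the dose test gives a confounded answer of unknown direction from about 15 people, with no stated method, and it contradicts the statement that all analyses are intention-to-treat. That dose is not randomised, that it varies after randomisation and that the statements conflict follow from the text; the imprecision follows from n = 15. The false-positive rates of about 6%, 15% and 48% rest on assumed correlations of 0.3, 0.5 and 0.7 without baseline adjustment. They show scale and do not forecast what this trial will find.

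A reader might conclude that the trial's efficacy result is compromised. It is not: the 6-month ViCCY versus HI comparison is by randomised group and does not use the session count.

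**What to change.** 1. In METHODS, 4, replace the sentence on testing by dose. Record scheduled sessions completed, boosters, and check-in calls that became sessions as three separate variables, and summarise each descriptively in the ViCCY arm.
2. If an association with outcome is reported, give it as an estimate with a 95% CI, adjusted for baseline score, labelled exploratory and non-causal, and not used to claim effectiveness by dose.
3. In STUDY PROCEDURES, 5, say that the efficacy analyses are intention-to-treat and that this exploratory summary is the exception.
4. Do not add an instrument-based per-session estimate.

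The cost is wording in two sections and separate REDCap fields for the three kinds of session, with no extra participants. The price is giving up any confirmatory dose-response statement, which this design could not support.

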Assessments of self-care, perceived stress, depression, burden, coping, relationship quality, and health status will be conducted at baseline (after enrollment but prior to randomization) and by phone at 3 and 6 months. We will also collect the credibility-expectancy scale at 1 month to evaluate treatment expectancy. Using contrasts within a mixed-effect modeling framework, we will assess intervention efficacy at 6 months using intention-to-treat analysis. We provide 10 health coaching sessions based on pilot data and literature demonstrating that a shorter duration of health coaching is not routinely effective. We chose to assess the primary aim at 6 months based on prior psychosocial intervention studies, but we will also assess outcomes at 3-months based on this rationale: baseline (enrollment), to generate consistent profiles of all enrollees at a consistent point in time and prior to implementation of the intervention; at 3-months to evaluate very early effects; and at 6-months to demonstrate efficacy of the intervention. Our goal is to establish preliminary efficacy and in a future study we will evaluate longer terms effects of ViCCY vs. HI at 6-months.

If a subject can no longer participate in the study safely or due to changes in circumstance that prevents participation (e.g., imprisonment, long term hospitalization, etc.) they will be withdrawn from the study. Data collection will not continue for participants who are withdrawn from the study. If applicable, research staff will arrange to collect study equipment from the participants who are withdrawing.

STUDY PROCEDURES:

1. Detailed Description:

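### Caregivers discontinued for non-adherence may have no further Self-Care Inventory scores, because the protocol does not separate stopping coaching from ending assessments

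*Combined protocol and SAP*

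**What the plan says.** **Removal.** Under Characteristics of the Study Population, section 5 (Early Withdrawal of Subjects), after allowing voluntary withdrawal: "They may also be discontinued from the study at the discretion of the Investigator for lack of adherence to intervention". The same sentence adds study procedures, visit schedules and adverse events as grounds. On follow-up it asks only this: "It will be documented whether or not each subject completes the study".

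**Data after withdrawal.** Methods, section 6 (Subject Follow-up) describes withdrawal in this case: "If a subject can no longer participate in the study safely or due to changes in circumstance that prevents participation". The next sentence carries no exception by reason: "Data collection will not continue for participants who are withdrawn from the study".

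**Analysis.** Study Procedures, section 5 (Statistical Analysis): "All analyses will use an intent-to-treat approach". Aim 1 makes the SCI the primary outcome. Efficacy is judged by a 6-month contrast in a mixed model.

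**Adherence.** Methods, section 4 on coaching: "We will track the number of sessions and test for differential effectiveness based on the dose received". On Health Information (HI): "Use of the website or book chapters will be used as a measure of fidelity in both arms".

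**Blinding.** Methods, section 3: "Investigators and all staff involved in collecting assessment data will be blinded to group assignment until after the data are locked".

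**Missing data.** Statistical Analysis plans baseline adjustment, a comparison of withdrawal rates and times, shared-parameter or pattern-mixture models with sensitivity analyses, and covariates to account for informative dropout. A complete-data analysis is allowed if loss is small (5%) and completely at random.

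**The concern.** An intention-to-treat contrast at 6 months needs a 6-month score from as many randomised caregivers as possible, whether or not they took up the intervention. Here poor uptake can itself end a caregiver's follow-up. Two analyses are exposed.

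- **Primary contrast.** Missed coaching can occur only in the ViCCY arm, so this ground for removal can differ by arm. If it does, and less adherent caregivers have worse self-care, the caregivers still observed in ViCCY are a favourable selection and the comparison leans towards ViCCY.
- **Dose-received analysis.** It depends on outcomes from caregivers with few sessions, the group most exposed to removal.

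This does not contradict the intention-to-treat statement. It means that scores the statement relies on may never be collected.

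**Working it through.** **1. The text, side by side.** Early Withdrawal of Subjects makes non-adherence a ground for leaving the study. Subject Follow-up ends data collection for anyone withdrawn. That sentence follows withdrawals for safety or changed circumstances, so applying it to non-adherence is an inference, but it is unqualified and the non-adherence rule sits under a withdrawal heading. The nearest other texts do not fill the gap. Methods section 4 counts sessions without a follow-up rule, and Risk/Benefit Assessment section 1 shortens data collection only for fatigue or stress.

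**2. The plan's own figure.** Target Population and Accrual claims over 90% power with 15 per arm. It cannot be reproduced, because no effect size, SD, visit correlation or dropout rate is given. Back-solving, two-sided at 5% and unadjusted:

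d = (1.960 + 1.282) × √(2/15) = 1.18 SD (1.23 with the t distribution), with all 30 observed.

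**3. Loss against the 5% condition.** 0.05 × 30 = 1.5 caregivers. One loss is 1/30 = 3.3%; two are 6.7%; three are 10%. Two losses take the trial outside its own condition for a complete-data analysis.

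**4. Precision.** If k caregivers are lost from one arm, the standard error grows by √[(1/(15−k) + 1/15)/(2/15)] = 1.02, 1.04, 1.06 for k = 1, 2, 3. With d = 1.18, power is Φ(d/√(1/15 + 1/(15−k)) − 1.960). It falls from 90% to 89.0%, 87.8% and 86.3%.

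**5. Bias with no true effect.** Assumptions, none from the documents: normal SCI with unit SD; correlation r = 0.6 between visits; adherence correlated ρ = 0.3 to 0.7 with the 3- and 6-month SCI and r × ρ with baseline; 6-month SCI regressed on group and baseline, as an approximation to the planned mixed model. The standard error with no loss is about √[(1 − 0.36) × 2/15] = 0.29, and close to 0.30 in simulation.

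Suppose the k least adherent of 15 are removed from ViCCY only, before the 3-month call. The expected values of the three lowest of 15 standard normal values are −1.736, −1.248 and −0.948. Mean adherence among those left rises by m = (sum of the k values, sign reversed)/(15 − k), and bias ≈ m × (1 − r²) × ρ.

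- k = 1: m = 1.736/14 = 0.124; bias 0.124 × 0.64 × (0.3 to 0.7) = 0.02 to 0.06
- k = 2: m = 2.984/13 = 0.230; bias 0.04 to 0.10
- k = 3: m = 3.932/12 = 0.328; bias 0.06 to 0.15

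Simulation (40,000 trials per setting) agrees:

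| Setting | Bias towards ViCCY (SD) | Type I error |
|---|---|---|
| None removed (check) | 0.00 | 4.5% to 5.0% |
| k = 1, ViCCY only | 0.02 to 0.06 | 5.1% to 5.6% |
| k = 2, ViCCY only | 0.04 to 0.10 | 5.4% to 6.7% |
| k = 3, ViCCY only | 0.06 to 0.15 | 5.6% to 7.9% |
| k = 3, 3-month SCI retained | 0.04 to 0.10 | 4.9% to 6.1% |
| k = 3, with a covariate correlated 0.5 with adherence | 0.05 to 0.12 | 5.5% to 6.9% |
| k = 3, removal only partly tied to adherence (0.5) | 0.03 to 0.08 | 5.0% to 5.6% |
| k = 2, removal only partly tied to adherence (0.5) | 0.02 to 0.05 | 4.9% to 5.3% |
| 3 in ViCCY, 1 in HI | 0.04 to 0.10 | not tabulated |
| 3 in each arm | 0.00 | 5.4% to 6.1% |

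Varying r from 0.4 to 0.8 moves the k = 3, ViCCY-only bias to between 0.03 and 0.20 SD.

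**The case against.** The case for leaving the text alone has real substance.

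- **Removal is discretionary and the link is inferred.** Nothing obliges the Investigator to remove anyone for missed coaching, and the stop sentence follows cases such as imprisonment or long hospitalisation. This stands. But on the narrow reading the protocol is still silent on whether a caregiver discontinued for non-adherence gets the remaining calls, so the same clarification is needed.
- **The plan promises effort towards complete data.** Statistical Analysis says so in general terms, and there are newsletters and a completion payment to support retention. The dose-received analysis also suggests that low-dose caregivers are expected to stay. None of this overrides an explicit rule that stops data collection.
- **Blinding limits any imbalance.** A blinded Investigator cannot act on missed coaching without learning the arm, and other kinds of non-adherence arise in both arms. This stands: the imbalance may be small.
- **The missing-data methods already cover it.** They help. But they rest on assumptions that the observed data cannot test, 30 caregivers give little information to fit them, and they cannot replace scores never collected.
- **The computed effect is modest.** This also stands. The upper figures need one-sided removal of exactly the least adherent caregivers before the 3-month call. Part of the excess type I error is not bias, since three removals in each arm give 5.4% to 6.1% with no bias. The 5% figure is a condition for choosing an analysis, not a tolerance limit.
- **A rule may exist elsewhere.** Operating procedures and an operations manual are cited but are not part of the document. The protocol should still state the rule.

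**Conclusion.** The concern holds. As written, the rules allow the trial to stop collecting SCI scores from caregivers because they did not adhere, and no passage provides for their 3- and 6-month assessments.

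The likely effect is small to moderate. In the near-worst case of three one-sided removals, the bias is a fifth to a half of a standard error (0.06/0.30 to 0.15/0.30). It is smaller if the 3-month score is kept or removal is only partly tied to adherence. It is negligible for one loss and zero for equal removals, where the cost is essentially precision.

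Size and direction both depend on the assumed removal counts, their split by arm, and the adherence and visit correlations. The gap should be fixed because the loss is avoidable, bears on the primary contrast of a 30-caregiver trial, and is cheap to prevent. It does not invalidate the design. Confidence is medium.

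**What to change.** In Early Withdrawal of Subjects and Subject Follow-up:

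1. State that stopping coaching, or non-adherence, does not by itself end assessments. When coaching stops remains a matter for the investigators.
2. Attempt the 3- and 6-month calls, collecting at least the SCI, for every randomised caregiver. Except only those who withdraw consent for contact or cannot safely or practically be contacted, which covers the cases already described in Subject Follow-up.
3. Record the reason for each discontinuation by arm, alongside the completion status and withdrawal timing already planned.

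A minor separate alignment: the Fatigue paragraph in Risk/Benefit Assessment section 1 gives health self-care neglect as its example of essential data. Naming the SCI there would ensure that a shortened call collects the primary outcome. The Stress paragraph already refers to the primary outcome variable.

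The cost is protocol and consent wording, plus a few extra phone assessments by staff who already make these calls. Some discontinued caregivers will still decline, so some loss will remain and the planned sensitivity analyses are still needed.

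### A random intercept plus random slope is over-parameterised for the two post-baseline visits, so the plan should fix the response vector and covariance structure before database lock

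*Combined protocol and SAP*

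**What the plan says.** STUDY PROCEDURES, 5. Statistical Analysis covers the primary Self-Care Inventory outcome and all secondary outcomes: "separate mixed effects regression models will be generated with SAS Proc Mixed". It then states that "Both random slopes and random intercepts will be modeled to represent deviations from the average, or fixed-effect, slope over time", and "REML will be used for parameter estimation and the most appropriate covariance structure will be examined". On baseline it says "Scores will be analyzed as repeated observations, with mean-centered baseline outcome scores serving as a covariate". The predictors are group, time and their interaction, and the interaction is named as the effect of main interest. AIC is to be used for overall fit and for choosing the pattern of change over time.

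METHODS, 6. Subject Follow-up gives the schedule. The outcome assessments "will be conducted at baseline (after enrollment but prior to randomization) and by phone at 3 and 6 months". The only other contact with a questionnaire does not measure self-care: "We will also collect the credibility-expectancy scale at 1 month to evaluate treatment expectancy". The same section places the efficacy test at month 6: "Using contrasts within a mixed-effect modeling framework, we will assess intervention efficacy at 6 months using intention-to-treat analysis".

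The plan does not say whether the two random effects are correlated, how time is coded, whether the baseline score also stays in the response, or what happens if the random-slope model does not converge.

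**The concern.** Once baseline moves to the right-hand side, two scores per caregiver are left. Two scores cannot separate a caregiver-specific slope from measurement error unless a further restriction is imposed, and the plan states none. The specified model therefore does not suit the specified schedule.

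In practice the software may stop, warn, or set a component to zero. The analyst must then choose another structure with the data in view, in a trial of 30 caregivers. If the model reduces to a random intercept alone, the month-3 and month-6 variances are assumed equal, and the standard error of the 6-month contrast is wrong to the extent that they differ.

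**Working it through.** **Inputs from the documents.** Responses at months 3 and 6 (Subject Follow-up); baseline as covariate, random intercept and slope, REML (Statistical Analysis); 30 caregivers, 15 per arm (Target Population and Accrual). The documents give no variances or correlations, so those below are assumptions. The stated power of over 90% has no bearing on identifiability. It also cannot be reproduced, because no effect size or standard deviation is given.

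**Step 1: correlated effects.** Let the intercept variance be a, the slope variance b, their covariance c and the residual variance s. With time coded 3 and 6:

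- Var(Y3) = a + 6c + 9b + s
- Var(Y6) = a + 12c + 36b + s
- Cov(Y3,Y6) = a + 9c + 18b

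That is three equations in four unknowns, and the rank is 3. Combining them gives Var(Y3) + Var(Y6) - 2Cov(Y3,Y6) = 9b + 2s, so b and s trade off freely. Assume both variances are 100 and the covariance is 60. Then 80 = 9b + 2s, or b = (80 - 2s)/9:

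| s | b |
|---|---|
| 10 | 6.67 |
| 20 | 4.44 |
| 30 | 2.22 |
| 38 | 0.44 |

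Each row has a valid (positive definite) random-effects matrix and gives back exactly the same 2x2 covariance, hence the same likelihood.

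**Step 2: what this does to the treatment effect.** In one simulated trial of 30, fixing the residual variance at 0.01, 0.05 or 0.10 gave the same REML criterion (18.88579) with slope variances of 0.032, 0.023 and 0.012. The group-by-time estimate (0.298, SE 0.203) and the 6-month contrast (0.534) were identical in all three fits.

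**Step 3: uncorrelated effects (c = 0).** Three equations, three unknowns:

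- b = [Var(Y6) - Var(Y3)]/27
- a = Cov(Y3,Y6) - 18b
- s = Var(Y3) - a - 9b

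The slope variance is now only a rescaled difference between two visit variances. It is set to zero whenever Var(Y6) is below Var(Y3). With 28 caregivers (assumed: 30 less two lost), that happened in about 50% of simulated trials with equal true variances. It happened in 26-30% with the month-6 variance 20% larger (correlation 0.5-0.7). Time coding matters: centring at the midpoint (-1.5, 1.5) drops the rank to 2, so even this version is not identified. Coding time as -3 and 0 gives Var(Y3) - Var(Y6) = 9b, which reverses the boundary condition.

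**Step 4: baseline kept as a response.** Three times give six quantities for four parameters (rank 4), so the model is identified. The baseline score would then be both outcome and covariate.

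**Step 5: effect on the 6-month test.** A random-intercept-only model uses the pooled variance [Var(Y3) + Var(Y6)]/2 where Var(Y6) is needed. With r = Var(Y6)/Var(Y3), the standard error is therefore off by a factor of sqrt[(1 + r)/(2r)]. Null simulations used 14 per arm, nominal two-sided 5%, t with 26 df, normal complete data, no baseline covariate and correlation 0.5-0.7:

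| r | SE factor | Random intercept only rejects | Unstructured rejects |
|---|---|---|---|
| 0.8 | sqrt(1.8/1.6) = 1.06 | about 4% | about 5% |
| 1.0 | 1.00 | about 5% | about 5% |
| 1.2 | sqrt(2.2/2.4) = 0.96 | about 5.5% | about 5% |
| 1.5 | sqrt(2.5/3) = 0.91 | about 7% | about 5% |
| 2.0 | sqrt(3/4) = 0.87 | about 8% | about 5% |

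The uncorrelated random-slope model rejects in about 3-4% of null trials at r = 0.67-0.8, and in 4.2-4.6% at r = 1.0-1.2.

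**The case against.** A reader might infer that the primary model cannot be fitted at all and that the primary result is lost. The documents do not support that, for four reasons.

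- Nothing in the plan says the random effects are correlated, and the uncorrelated version is just identified.
- The plan leaves the covariance structure open and mentions AIC, so some adaptation is intended.
- The plan does not state that baseline rows are excluded from the response. If they stay, all four parameters are identified.
- What is not identified is how the variance divides between intercept, slope and residual, and the plan does not set out to report that. The 15-fold spread in slope variance in Step 1 (6.67/0.44) concerns a nuisance quantity. Likewise, a 50% boundary frequency is not a 50% failure rate.

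The harm also depends on which effect is tested. With complete data and no baseline adjustment, the standard error of the group-by-time effect is the same under random-intercept-only and unstructured covariance, because both rest on Var(Y3) + Var(Y6) - 2Cov(Y3,Y6). The miscalibration in Step 5 applies to the 6-month contrast.

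All of this stands as a limit on the size of the point, but it does not remove it. The uncorrelated version depends on an unstated time coding. Keeping baseline as a response puts the same score on both sides of the model. Examining structures, with no candidate list and no fallback, leaves the choice until after the data are seen. AIC cannot separate solutions that have the same likelihood. Using actual visit dates as continuous time might identify the model formally, but only weakly.

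**Conclusion.** The point holds in a limited form. With baseline as a covariate only, which is the natural but unstated reading, the random-effects specification is over-parameterised for the visit schedule: four parameters against three quantities if the effects are correlated, and a fragile just-identified model if they are not. The group-by-time effect and the 6-month contrast remain estimable.

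The consequences are convergence or boundary problems, a data-dependent replacement structure, and modest error in the 6-month test. That error is small when the visit variances are within about 20% of each other. It reaches about 7-8% rejection at a nominal 5% when the model falls back to a random intercept and the month-6 variance is 1.5-2 times the month-3 variance. The uncorrelated model errs the other way, at about 3-4%, when the month-6 variance is the smaller.

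The parameter count follows from the documents. The percentages rest on assumed variances, correlations and complete data. This should be fixed before lock, but it does not invalidate the trial's primary test.

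**What to change.** State that the response vector is the month-3 and month-6 scores, with the baseline score as covariate only. Replace the random-intercept and random-slope sentence with wording such as: visit is a categorical factor; the within-caregiver covariance is an unstructured 2x2 matrix; estimation is by REML with Kenward-Roger degrees of freedom; no random effects are fitted. Apply this to the primary and secondary outcomes, and to Aim 2 wherever its response is limited to these two visits.

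A random intercept alone would also be identified, but it assumes equal variances at the two visits. The unstructured form avoids that assumption, does not depend on time coding, and stayed near 5% in every setting simulated.

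The cost is a short change of wording before lock, with the same SAS procedure and no new data. All that is given up is a slope-variance estimate that two visits cannot reliably supply.
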